5.2 Safety Analysis Set

A group of subjects who receive at least one dose of investigational drug is defined as the “safety analysis set (SAF)”. SAF will be used for the analysis of all subject characteristics, investigational drug administration and safety endpoints.

5.3 PK Analysis Set

The “PK analysis set (PKS)” will consist of all subjects who receive at least one dose of investigational drug and have at least one point of drug plasma or urine concentration data. PKS will be used for the analysis of PK endpoints.

6 HANDLING OF SUBJECTS AND DATA

Before the data is fixed to be analyzed, the project team will determine the handling of subjects.

If it is considered that data including laboratory values, 12-lead electrocardiogram (ECG) readings or drug plasma/urine concentration measurements has been affected by abnormality of a sample (e.g. hemolysis or milky fluid), a technical error, the project team will decide whether or not to exclude that data from analysis prior to the data-lock.

In case that medical judgement is required, the advice from sponsor’s medical experts including a cardiac safety advisor will be obtained.

7 ATTENTION ON ANALYSIS

7.1 Data for Statistical Analysis

Clinical data is collected from medical institution using electronic case report form (eCRF) or is electronically transferred from the central laboratory of drug plasma/urine concentration measurement and the central review organization of pathology and tumor response. The clinical data collected by eCRF or electronically transferred clinical data will be entered into database, cleaned, fixed and then used for statistical analysis. Data collection, input, cleaning and fixing are performed under responsibility of a study manager, clinical research associates and a data management person in charge. Fixed data is provided by a person in charge of data management to that of statistical analysis.

7.2 Descriptive Statistics

Following descriptive statistics will be summarized.

- Continuous variables
 - Number of available data, Mean, Standard deviation (SD), Median, First and third quartile points, Minimum and Maximum
- Categorical variables
 - Frequency and Percentage

7.3 Display Digit

- Mean, SD, median, first and third quartile points, and geometric average will be rounded to one more dps than the raw data.
- Minimum and Maximum data will be displayed as original decimal point of raw data.
- Percentages, Confidence Interval (CI) will be rounded to one decimal point.

7.4 Changes from the Protocol

We think that 65 would be more appropriate to consider the age standard of elderly in modern times, so we will change the age standard from 61 to 65.

8 STATISTICAL METHOD

8.1 Detail of Statistical Analysis

8.1.1 Significance Level and Confidence Interval

Tests with any significance level will not be performed. Confidence Interval will be calculated by Clopper-Pearson 'exact' method.

8.2 Consideration of Statistical Analysis

8.2.1 Adjustment by Covariates

Adjustment by covariates will not be performed.

8.2.2 Withdrawal and Missing

Analyses will be performed with no consideration for withdrawal of subjects. If date of birth is missing, values will be complemented as follows.

- If day is missing, 15 (middle of the month) will be completed.
- If day and month is missing, July 1 (middle of the year) will be completed.

The others will not be perform any imputation for missing value.

8.2.3 Interim Analysis and Data Monitoring

No interim analysis and no early termination for efficacy are planned in this study.

Interim evaluation for efficacy and safety including PK as needed (cf. Section 8.5.2 of Protocol) will be performed at the point when the number of efficacy evaluable subjects reaches 20 and necessary data is obtained from these subjects.

8.2.4 Multicenter Study

Analyses will be performed with no adjustment for Multicenter.

8.2.5 Adjustment for Multiplicity

Analyses will be performed with no adjustment for multiplicity.

8.2.6 Integrated Analysis

Not applicable.

9 SOFTWARE

All analyses will be performed using SAS® Ver9.2 (or later version).

10 SUBJECTS OF THE CLINICAL STUDY

10.1 Disposition of Patients

10.1.1 Subject Disposition

Numbers of subjects will be counted according to following terms.

- Informed consent obtained subjects
- Enrolled subjects
- Not-enrolled subjects
- Treated subjects
- Not-treated subjects
- Study Completion subjects
- Study Withdrawal subjects

10.1.2 Analysis Dataset

Numbers of subjects will be counted according to following terms.

- Efficacy analysis set of FAS
- Efficacy analysis set of PPS
- SAF
- PKS

10.1.3 Disposition of Withdrawn Subjects

Number of withdrawn subjects will be summarized with reasons for withdrawal.

10.1.4 Demographic and Other Baseline Characteristics

Descriptive statistics of following variables at screening period will be calculated by ethnic background (Japanese, Except Japanese, Korean, Taiwanese, Hong Konger/Chinese and others).

- Numerical Variables
 - Age (years)
 - Sum of the product of the greatest diameter (SPD) of target lesion (major axis and minor axis) (cm²)
 - Height (cm)
 - Weight (kg)
 - Body surface area (BSA) (m²)
(BSA (m²) = Weight (kg)^{0.425} × Height (cm)^{0.725} × 0.007184)
 - Number of prior medication (chemotherapy or immune therapy)
- Categorical Variables
 - Sex
 - Ethnic group/Race

- Eastern Cooperative Oncology Group (ECOG) Performance Status Scale
- Histopathological classification of lymphoma
- Clinical Symptom Caused by Primary Disease (Concomitant Symptom)
- Clinical stage by Ann Arbor Classification
- International Prognostic Index (IPI) risk group
- Prognosis Index for T-cell lymphoma (PIT) risk group
- Presence of prior medication (chemotherapy or immune therapy)
- Response to most recent therapy
- Presence of prior radiation therapy
- Presence of prior transplant of hematopoietic stem cell transplant
- Other therapy
- Presence of liver enlargement
- Presence of spleen enlargement
- Presence of bone-marrow infiltration
- Presence of Medical History
- Presence of Allergy and/or drug sensitivity
- Neurological and mental status assessments
 - Presence of finding of cranial nerve abnormalities
 - Presence of finding of sensory abnormalities
 - Presence of finding of motor abnormalities
 - Presence of finding of coordination (gait) abnormalities
 - Presence of finding of reflex abnormalities
 - Presence of finding of mental status abnormalities
- Presence of pregnancy

10.1.5 Compliance of Study Drug Administration

Compliance of SP-02L administration (number of administration completed and skipped) and total volume of administration will be summarized by cycle and all cycles in total and by ethnic background (Japanese, Except Japanese, Korean, Taiwanese, Hong Konger/Chinese and others).

11 EFFICACY EVALUATION

11.1 The Best Overall Response Based on Central Assessment

Based on a central assessment of tumor response by Efficacy and Safety Review Committee, the response up to Cycle 6 will be summarized to calculate the overall response rate (ORR), the disease control rate (DCR), the best overall response and their 90% Confidence Interval (90% CI) respectively, and count the number of subjects per cycle. A binomial test will be performed for the null hypothesis “true objective response rate is less than or equal to the threshold objective response rate of 0.1 that is assessed to be ineffective”.

The same analysis will be performed by histopathological classification (PTCL-not otherwise specified [PTCL-NOS], Angioimmunoblastic T-cell Lymphoma [AITL], Anaplastic Large Cell Lymphoma [ALCL] ALK-positive and ALCL ALK-negative, other lymphoma), clinical stage according to Ann Arbor classification (Stage I, Stage II, Stage III, Stage IV), prognosis risk group according to IPI, prognosis risk group based on PIT, response to most recent therapy (Yes (CR/CRu/PR), No (SD/PD), Unknown/Unable to assess), ethnic background (Japanese, Except Japanese, Korean, Taiwanese, Hong Konger/Chinese and others), sex and age (< 65 years old or ≥ 65 years old).

11.2 The Best Overall Response Based on Local Assessment

Based on a local assessment of tumor response at each investigational site, the same analysis described in 11.1 will be performed for the response up to Cycle 6.

11.3 Comparison of Best Overall Response between Central Assessment and Local Assessment

Based on the central assessment and local assessment of tumor response, cross tabulation will be performed for the best overall response up to Cycle 6 in total and by ethnic background (Japanese, Except Japanese, Korean, Taiwanese, Hong Konger/Chinese and others).

11.4 Other Tabulations for The Best Overall Response

Based on a local assessment of tumor response at each investigational site, the same analysis described in 11.1 will be performed for the response in the entire period.

To assess the tumor response in each subject, the waterfall plot will be produced to show the rate of tumor shrinkage at best overall response based on the central assessment and local assessment of tumor response in total and by ethnic background (Japanese, Except Japanese).

11.5 Percent Change from Baseline of Tumor Size

Based on the central assessment and local assessment of tumor size, the percent change from baseline will be plotted using Spider plot.

11.6 Analyses for Survival Time

PFS, TTR, DOR and OS will be summarized to calculate lower quartile, median, upper quartile and their 90%

CI by using Kaplan-Meier method in total and by ethnic background (Japanese, Except Japanese, Korean, Taiwanese, Hong Konger/Chinese and others). As for PFS and OS, Kaplan-Meier curve will be displayed. The same analysis will be performed by histopathological subtypes (PTCL-NOS, AITL, ALCL ALK-positive, ALCL ALK-negative, other lymphoma).

"Progressive disease (PD)", "Relapsed disease (RD)" or "death" which occurs earlier is defined as "progression event", and "the date of progression" will be identified for analyses of PFS and DOR in accordance with the following rules:

- The date of judgment of PD or RD based on the local assessment of tumor response by investigator at each site (cf. Section 6.14.2 of protocol) is defined as "the date of progression".
- PD or RD includes not only the results of tumor response assessment based on diagnostic imaging data but also investigator's clinical judgment of "Symptomatic Progression" based on clinical symptoms and findings, and clinical laboratory test result, etc.). In this case, the date of the judgement is defined as "the date of progression".
- If "death" occurs earlier than the judgement of "PD" or "RD", the date of death is defined as "the date of progression".

If no progression event is confirmed prior to the following events, the most recent date of local assessment of tumor response will be defined as "the date of censoring":

- Subsequent therapy for primary disease is initiated
- Investigational drug is withdrawn due to adverse drug reaction
- Subject is lost to follow up

If a subject is surviving on the date of data cut-off, the most recent date of confirmation of subject's existence is defined as "the date of censoring" for the analysis of OS. For a subject lost to follow-up, the last date when the subject's existence is confirmed prior to the subject's lost to follow-up is defined as "the date of censoring". If treatment-duration exceeds 2 years, the date after 2 years is defined as "the date of censoring".

12 SAFETY EVALUATION

Following analyses will be performed on SAF except 12.2.5 and 12.2.5 will be performed on PKS.

12.1 Adverse Event

12.1.1 Summary of Adverse Events

Number of subjects with AE will be counted according to following terms in total and by ethnic background (Japanese, Except Japanese, Korean, Taiwanese, Hong Konger/Chinese and others).

- AE
- Serious AE
- Adverse drug reaction
- Serious Adverse drug reaction
- AE leading to withdrawn from the study
- Adverse drug reaction leading to withdrawn from the study
- AE of NCI-CTCAE Grade 3 or higher
- Adverse drug reaction of NCI-CTCAE Grade 3 or higher

12.1.2 Number of Subjects with Any Adverse Event

The occurrence of AEs will be summarized by system organ class and by preferred term according to the Medical Dictionary for Regulatory Activities (MedDRA) dictionary, and by ethnic background (Japanese, Except Japanese, Korean, Taiwanese, Hong Konger/Chinese and others) and by severity.

The bar graph will be produced to show the occurrence of AEs by severity.

When one subject experiences same PT of AE more than once, the severest event will be counted (National Cancer Institute Common Terminology Criteria for Adverse Events [NCI-CTCAE] Grade 1 < Grade 2 < Grade 3 < Grade 4 < Grade 5). Adverse event of NCI-CTCAE Grade 3 or higher will be also summarized in the same way.

12.1.3 Number of Subjects with Adverse Drug Reaction

An adverse drug reaction is defined as an AE with possible relationship with the investigational drug.

The same analyses described in 12.1.2 will be performed for adverse drug reaction.

12.1.4 Number of Subjects with Any Serious Adverse Event

The same analyses described in 12.1.2 except graph will be performed for serious AE.

12.1.5 Number of Subjects with Serious Adverse Drug Reaction

The same analyses described in 12.1.2 except graph will be performed for serious adverse drug reaction.

12.1.6 Number of Subjects with Adverse Event of Special Interest

The same analyses described in 12.1.2 except graph will be performed for AESI. AESI is defined AEs that will be coded as “Psychiatric disorders”, “Nervous system disorders” or “Hepatobiliary disorders” of system organ class according to the MedDRA dictionary.

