1.2.4. Known and Potential Risks

A total of 164 subjects received the investigational drug in 6 clinical studies conducted by ZIOPHARM. The integrated analysis includes all safety data collected and in the clinical data base as of March 31, 2012. Adverse events (AEs) occurring $\geq 5\%$ of subjects across all studies that were reported by the investigator as being at least possibly related to investigational drug include nausea (20%), fatigue (18%), dizziness (9%), anemia (8%), vomiting (8%), headache (8%), confusional state (6%), diarrhea (5%), anorexia (5%), hypomagnesemia (5%), hyperglycemia (5%), and infusion site pain (5%). Of all Grade ≥ 3 AEs that were considered possibly related to investigational drug, those occurring in ≥ 2 subjects include fatigue (4%), hyperglycemia (4%), anemia (2%), febrile neutropenia (2%), neutropenia (2%), coordination abnormal (2%), confusional state (2%), infusion site pain (1%), hypoglycemia (1%), hypokalemia (1%), hypophosphatemia (1%), mental status changes (1%), and hypoxia (1%).

In two phase 1 studies conducted by Solasia Pharma K.K. respectively in Japan and Korea in subjects with PTCL (Study SP-02L01 and SP-02L03), 23 subjects received the investigational drug. A integrated analysis of these two clinical studies indicated that investigational-drug-related AEs, occurring in ≥ 2 subjects, included constipation (17%), nausea (17%), malaise (17%), pyrexia (17%), alanine aminotransferase increased (17%), aspartate aminotransferase increased (17%), activated partial thromboplastin time prolonged (17%), decreased appetite (13%), somnolence (13%), platelet count decreased (13%), herpes zoster (9%), lymphopenia (9%), hallucination (9%), white blood cell count decreased (9%), neutrophil count decreased (9%), C-reactive protein increased (9%), and blood alkaline phosphatase increased (9%). Grade ≥ 3 investigational-drug-related AEs occurred in 4 of 23 subjects (17%), and included neutrophil count decreased (9%, 2 subjects), platelet count decreased (9%, 2 subjects), diffuse large B-cell lymphoma (4%, 1 subject), anaemia (4%, 1 subject), febrile neutropenia (4%, 1 subject), lymphopenia (4%, 1 subject), nausea (4%, 1 subject), hepatic function abnormal (4%, 1 subject), lymphocyte count decreased (4%, 1 subject), white blood cell count decreased (4%, 1 subject), and activated partial thromboplastin time prolonged (4%, 1 subject).

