One subject who received 300 mg/m² of the investigational drug once daily for 5 consecutive days followed by 16 days rest (3-week cycle) in Japan phase 1 study (Study SP-02L01) had a report of hepatic function disorder (Grade 3) which was determined as a Dose-Limiting Toxicity (DLT). The maximum tolerated dose (MTD) was not identified in either of these studies. The integrated analysis was conducted for the efficacies (tumor responses) of the investigational drug in 14 subjects who completed at least 2 cycles and had a tumor response assessment. The best overall response in the efficacy analysis set were complete response (CR) in 1 subject, partial response (PR) in 3 subjects, stable disease (SD) in 6 subjects and progressive disease (PD) in 4 subjects. Five of 6 subjects with stable disease showed tumor shrinkage to some extent.

As described above, based on the previous clinical studies, no serious concern regarding safety of SP-02L was indicated, and preliminary tumor responses in patients with PTCL were confirmed, suggesting that the clinical development of SP-02L is positively significant for the treatment of this disease.

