12.1.7 Number of Subjects with Any Grouping Adverse Event

The occurrence of AEs will be summarized by any grouping Adverse Event, preferred term according to the MedDRA dictionary, and by ethnic background and by severity. Grouping Adverse Event is following.

Grouped Term	Preferred Terms
Fatigue/malaise	Fatigue, Malaise
Hepatic function test abnormal	Aspartate aminotransferase increased, Alanine aminotransferase increased, Gamma-glutamyltransferase increased
Anaemia	Anaemia, Haemoglobin decreased
Thrombocytopenia	Thrombocytopenia, Platelet count decreased
Neutropenia	Neutropenia, Neutrophil count decreased
Lymphopenia	Lymphopenia, Lymphocyte count decreased
Leukopenia	Leukopenia, White blood cell count decreased
Injection site reaction	Infusion site pain, Injection site pain, Injection site reaction, Injection site rash, Infusion site pruritus, Infusion site rash
Hyperglycaemia	Hyperglycaemia, Blood glucose increased
Taste disorder	Taste disorder, Dysgeusia
Hyperbilirubinaemia	Hyperbilirubinaemia, Blood bilirubin increased
Hypoalbuminaemia	Hypoalbuminaemia, Blood albumin decreased
Hypomagnesaemia	Hypomagnesaemia, Blood magnesium decreased
Hyponatraemia	Hyponatraemia, Blood sodium decreased
Hypokalaemia	Hypokalaemia, Blood potassium decreased
Catheter site related reaction	Catheter site pain, Catheter site related reaction, Catheter site haemorrhage, Catheter site erythema, Catheter site bruise, Catheter site pruritus, Catheter site rash, Catheter site oedema, Catheter site discharge, Catheter site swelling
Abdominal pain	Abdominal pain, Abdominal tenderness, Abdominal pain lower, Abdominal pain upper
Sepsis/Bacteraemia	Sepsis, Bacteraemia, Enterococcal bacteraemia, Escherichia sepsis, Pseudomonal sepsis, Device related sepsis, Neutropenic sepsis, Staphylococcal bacteraemia

Grouped Term	Preferred Terms
Neuropathy peripheral	Neuropathy peripheral, Peripheral sensory neuropathy

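### SAP 12.1.6 defines hepatic AESI by organ class alone, so the AESI table probably omits transaminase and bilirubin rises, and no planned table counts subjects with any hepatic event

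*SAP*

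**What the plan says.** SAP 12.1.6 begins "The same analyses described in 12.1.2 except graph will be performed for AESI. AESI is defined AEs that will be coded as" and goes on to name three organ classes. The definition is the second of its two sentences: "AESI is defined AEs that will be coded as “Psychiatric disorders”, “Nervous system disorders” or “Hepatobiliary disorders” of system organ class". AESI are then tabulated as in SAP 12.1.2, without the graph: by organ class, preferred term, ethnic background and severity. The section names no preferred terms and does not refer to the grouped terms of 12.1.7.

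SAP 12.1.7 separately defines a group called Hepatic function test abnormal, made up of "Aspartate aminotransferase increased, Alanine aminotransferase increased, Gamma-glutamyltransferase increased". Bilirubin terms form another group, Hyperbilirubinaemia. Section 12.1.8 repeats the grouped tables for adverse drug reactions.

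The phase 1 background is in the protocol. Section 1.2.4 pools two studies in which "23 subjects received the investigational drug" and gives 17% each for drug-related ALT increased and AST increased. Its list of drug-related events of Grade 3 or higher includes "hepatic function abnormal (4%, 1 subject". Section 1.3.1 says that one subject "had a report of hepatic function disorder (Grade 3) which was determined as a Dose-Limiting Toxicity (DLT".

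Protocol 9.4.4 leaves significant AEs to the sponsor's judgement and gives only neurological and psychiatric examples. The hepatic component is therefore an addition made by the SAP.

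**The concern.** Having made the liver a special interest, the SAP uses a rule that depends on how the event is worded. A liver injury recorded as hepatic function abnormal would count. The same injury recorded as ALT increased would not, if that term is coded as a laboratory finding. In phase 1 the laboratory wording was the commoner one.

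The AESI table is where a reader would look first for the hepatic rate. Because it is also split by ethnic background, recording habits that differ between Japan, Korea, Taiwan and Hong Kong could look like ethnic differences in hepatic risk. The other tables do not supply the missing figure, which is the number of subjects with at least one hepatic event of any kind.

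**Working it through.** **Inputs** (Protocol 1.2.4, drug-related events, 23 subjects): ALT increased 17%; AST increased 17%; blood alkaline phosphatase (ALP) increased 9%; hepatic function abnormal, Grade 3 or higher, 1 subject (4%).

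**1. Reproduce the stated percentages.** 4/23 = 17.4% (stated 17%); 2/23 = 8.7% (stated 9%); 1/23 = 4.3% (stated 4%). The counts are therefore 4, 4, 2 and 1.

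**2. Where the laboratory terms are coded.** The documents do not print the MedDRA hierarchy, so this is an assumption. Two places support it.
- Within each frequency band of Protocol 1.2.4 the terms appear to run in organ-class order. In the Grade 3 or higher list, hepatic function abnormal comes directly after nausea and before the laboratory terms. In the 17% band, ALT and AST increased do not follow nausea; they come after malaise and pyrexia and next to APTT prolonged, a laboratory term.
- SAP 12.1.7 pairs disorder terms with laboratory terms for the same toxicity (Anaemia with Haemoglobin decreased, Hyperbilirubinaemia with Blood bilirubin increased). The SAP itself thus expects one toxicity to be coded in two ways.

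**3. Phase 1 count under each rule.** The number of subjects with any of several events lies between the largest single count and the sum of the counts.
- Organ class only: 1/23 = 4.3%.
- Organ class plus ALT and AST: from max(1, 4, 4) = 4 to 1 + 4 + 4 = 9, so 4/23 to 9/23, or 17.4% to 39.1%.
- With ALP as well: from 4 to 9 + 2 = 11, so 17.4% to 47.8%.

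On the ALT/AST definition, the organ-class rule shows between one quarter (1/4) and one ninth (1/9) of the subjects.

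**4. Scale to 65 subjects, for illustration.** 65 × 1/23 = 2.8; 65 × 4/23 = 11.3; 65 × 9/23 = 25.4. Exact 95% limits are 0.1% to 21.9% for 1/23 and 5.0% to 38.8% for 4/23, which is about 0 to 14 and 3 to 25 of 65. The ranges overlap widely.

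**5. What each planned table gives.**

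| SAP section | Hepatic content |
|---|---|
| 12.1.2, 12.1.3 | Every AE and every drug reaction by organ class and preferred term |
| 12.1.6 | Hepatobiliary organ class only |
| 12.1.7, 12.1.8 | AST, ALT and GGT as one group, bilirubin as another; neither contains hepatic function abnormal or ALP |
| 12.2.1 | AST, ALT, ALP and bilirubin values and changes by time point |

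The number with either kind of event is the 12.1.6 count plus the 12.1.7 counts, minus the subjects in more than one row. That overlap is not tabulated, so the rows cannot be added. The worst-grade rule in 12.1.2 works per preferred term, so it does not give a subject's worst hepatic grade across terms.

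**The case against.** The strongest reply is that nothing is hidden. Transaminase events appear in 12.1.2, 12.1.3, 12.1.7 and 12.1.8, including by severity and ethnic background, and liver values are summarised in 12.2.1. The AESI definition is openly stated. This stands. A reader might infer that transaminase rises go unreported or that the trial's overall hepatic risk will be understated, and the documents support neither.

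A reader might also infer that the rule would miss the phase 1 dose-limiting event. It would not. That event was a "hepatic function disorder (Grade 3) which was determined as a Dose-Limiting Toxicity (DLT"), which matches the single Grade 3 or higher hepatic function abnormal case, and on the same coding assumption the organ-class rule captures it. No Grade 3 or higher ALT or AST rise is listed. The transaminases are the leading hepatic signal by frequency, not by severity.

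Protocol 7.1.1 asks investigators to record a diagnosis where possible, and to record the disease rather than the laboratory finding when both are present. That makes an organ-class AESI for diagnosed hepatic disorders coherent and reduces variation in wording. It does not remove it: a transaminase rise with no accompanying diagnosis remains a laboratory term, and 12.1.7 plans for such terms.

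The phase 1 figures are also a weak base. They mix 200 and 300 mg/m² and two cycle lengths. They cover drug-related events only, whereas 12.1.6 counts all AEs. The all-grade list omits events seen in a single subject, so 1/23 is a minimum. Finally, no test, stopping rule or sample-size figure depends on the AESI table.

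**Conclusion.** The definitional gap stands, limited to the AESI table. Following SAP 12.1.6 as written gives a hepatic AESI count that leaves out the most frequent drug-related hepatic terms of phase 1: 1/23 documented under the rule, against 4/23 to 9/23 once ALT and AST are included. No planned table supplies the combined count.

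This rests on the assumption that liver laboratory terms are coded outside Hepatobiliary disorders, which the documents indicate but do not state. The direction does not depend on the phase 1 numbers, since adding terms can only keep or raise the count. The size does depend on them, and about 3 against 11 to 25 of 65 subjects is an illustration, not a forecast. The primary endpoint is unaffected. Severity is minor to moderate.

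**What to change.** In SAP 12.1.6, define hepatic AESI as the organ class Hepatobiliary disorders plus the preferred terms of the 12.1.7 groups Hepatic function test abnormal and Hyperbilirubinaemia, plus blood alkaline phosphatase increased. A standard hepatic MedDRA query would serve instead. Count each subject once, at worst grade across all hepatic terms, for all AEs and again for drug-related AEs. Keep the organ-class-only count as a sub-row, so that diagnosed disorders remain distinguishable from laboratory-only changes.

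The cost is a wording change and one reprogrammed table with an extra row; no new data are needed. The downside is a less favourable hepatic AESI rate that includes changes seen only in the laboratory.
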